#### Measures for Aim 1 (Pain scores)

The primary outcome of this study will be composite pain scores 24 hours after surgery. Others have shown that composite pain scores quantify pain with greater accuracy than a single measurement. Jensen et. al. concluded in their study that composite pain intensity scores from two or more individual ratings of pain are valid for detecting treatment effects. Pain scores will be measured using a numeric rating scale (NRS) (0=no pain; 10= worst possible pain). "Worst," "average," and

“least” pain scores will be assessed for the preceding time interval at 24, 48, and 72 hours following surgery. Inpatient pain scores will be collected as part of routine post-operative care and will be extracted from the medical record; there is no set protocol for routine pain score collection but typically it is done every 4-8 hours. To collect pain scores, nursing staff asks patients to rate their current pain on a scale from 0-10. If a participant is discharged prior to 72 hours after surgery, NRS scores will be assessed at the remaining time points via telephone. Prior to discharge, study staff will provide patients with a log to keep a record of their pain scores, at least once every 8 hours, in order to mitigate recall bias in anticipation of being contacted by research staff. Study staff will call discharged patients and ask them to report their pain scores for each 24 hour period between discharge and 72 hours postoperatively as recorded on the forms they were given at time of discharge.

#### Measures for Aim 2 (Opioid consumption)

For our opioid consumption assessments, data will be collected intraoperatively, in the PACU and at the 24hr, 48hr and 72hr timepoints following surgery. Information on opioid type and dose will be obtained through review of the participant’s electronic medical record or through phone assessment, depending on point of hospital discharge. Opioid amounts will be converted into MMEs. Patients who are discharged prior to 72 hours after surgery will be given a log to record the pain medications they consume during that period. Study staff will call patients to collect this data.

#### Measures for Aim 3 (Depression and OUD severity)

To evaluate depression severity, we will use the patient health questionnaire (PHQ-9), a validated screening tool used to monitor depressive symptoms. For our OUD severity assessments, we will administer the Desires for Drug questionnaire (DDQ) and the opioid craving scale (OCS) to determine level of opioid cravings, the current opioid misuse measure (COMMS) to detect opioid misuse, and a 30-day Timeline Follow-Back questionnaire (<https://www.smashlabs.org/timeline>) to obtain a quantitative estimate of substance use in the month prior to surgery.

Timeline Follow-Back is a commonly used, validated tool in behavioral research; it is a calendar based method of collecting self-reported use of illicit substances.

We will compare the pre-operative and 30-day postoperative participant responses

to the above instruments to assess differences between the +BUP and –BUP groups. On the day of surgery, we will also administer the clinical opioid withdrawal scale (COWS) to detect opioid withdrawal.

#### Measures for Aim 4 (Opioid Dispensing)

For our assessments on outpatient opioid utilization during the 30 days following surgery, we will review each participant's Maine Prescription Awareness Tool (MainePAT). MainePAT is part of the monitoring program that tracks all schedule II-V medications prescribed in Maine, Massachusetts and Rhode Island. Using this resource, we will collect data on the number of opioid agonist prescriptions filled and the total amounts of opioids (in MME) dispensed. Buprenorphine formulations will not be included in our MME totals.

#### ***Subject Selection***

Inclusion Criteria: Male or female; aged 18-75 years; American Society of Anesthesia (ASA) health class I-III; currently taking buprenorphine formulations equivalent to 12mg or greater for at least the prior 30 days for treatment of OUD (as defined by the Diagnostic and Statistical Manual of Mental Disorders- 5 (DSM-V) criteria); scheduled for surgery at MMC or SSC where a procedure with a greater than 4/10 intensity is expected on POD 1 (see Gerbershagen et.al. and appendix 1 for list of surgeries).

Exclusion Criteria: Unable to consent to the study; currently pregnant; current major medical illness that could limit the ability to utilize medications within our protocol driven multimodal analgesic plan (e.g. cancer, severe end-stage organ disease, or dementia).

Inclusion of women and minorities. We will not exclude any adults on the basis of age, gender or ethnicity and our projected enrollment is based on most recent Maine census. See appendix 2 for projected enrollment table.

Inclusion of individuals across the lifespan. We will exclude individuals under the age of 18 years from enrollment in this trial. These patients require personalized treatment strategies often coordinated by multiple providers therefore we will not alter these treatments decisions for study purposes.

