## Background

Opioid use disorder (OUD) is a chronic neurobehavioral disease characterized by continued opioid use despite the desire to quit, often punctuated by cycles of remission and opioid use relapse. OUD is associated with high rates of medical comorbidity and life expectancy is two decades shorter when compared to those without OUD. In the past 20 years, opioid related deaths have risen exponentially. Maine has been especially devastated by this trend and, although OUD mortality rates declined in 2018, they are beginning to re-ascend. It is projected that the overdose death rates for 2020 will be the highest on record, as the first quarter of this year has seen a 23% increase in opioid related mortality. Unfortunately, despite our national crisis, opioids remain prominent in perioperative

analgesic regimens for the millions of surgeries and procedures performed each year in the United States.

Opioid maintenance therapy (OMT) with buprenorphine has reduced hospitalization rates and mortality for those with OUD. The optimal duration of OMT has not been established and relapse rates can be high when OMT is discontinued. A multi-site study sponsored by the National Institute on Drug Abuse (NIDA) reported relapse rates approaching 90% following the premature discontinuation of OMT.

Clinical opinion is mixed on whether buprenorphine should be held, continued at full dose, or reduced in the perioperative period as it is limited to case reports, case series and provider opinion. Acute post-surgical pain management can be challenging in these patients when standard pain regimens, including full mu opioid receptor agonists, are needed for post-operative pain management.

Buprenorphine has high receptor binding affinity, a long half-life, and displays partial mu opioid receptor agonism- all properties which can prevent effective analgesia from full mu opioid agonists used in conjunction for pain control.

Therapeutic doses of buprenorphine for OUD treatment (16-32mg) are thought to saturate opioid receptors, rendering further opioid use for analgesia ineffective.

There are published reports of patients with poorly controlled postoperative pain when buprenorphine was continued and some providers recommend buprenorphine discontinuation at about 72 hours prior to elective surgery and replacement with low dose opioid agonists to reduce the risk of opioid withdrawal.

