There are preclinical data and evidence from patients taking buprenorphine for chronic pain at analgesic doses that the addition of opioid agonists is effective in treating breakthrough pain. Neuroimaging of opioid receptor availability in heroin dependent patients receiving buprenorphine suggest that 8mg of buprenorphine is the ideal dose where receptors are available for additional opioid agonists to bind and facilitate analgesia. We compiled this evidence to establish institutional guidelines to continue buprenorphine at an 8mg analgesic dose. We subsequently published a retrospective observational study about our experience with analgesic dosed buprenorphine continuation compared to discontinuation. We identified that outpatient opioid dispensing and PACU pain scores were significantly higher in the cohort where buprenorphine was discontinued compared to when it was continued. A recent retrospective study from Stanford University published similar findings, reporting that patients continued on buprenorphine perioperatively at varied tapered doses received significantly less opioid prescriptions without changes in pain scores when compared to patients where buprenorphine was discontinued. These clinical observations challenge previous assumptions that, due to its pharmacology, buprenorphine interferes with opioid based pain management. However, these studies are limited by their retrospective, non-randomized design, and their absence of controlled clinical conditions; also, they do not address relapse rates and postoperative OUD-related symptoms. Most importantly, current established

national guidelines are to continue buprenorphine without dose adjustment or to discontinue buprenorphine perioperatively, without evidence to support either strategy. The current national guidelines disclose that full dose buprenorphine continuation can lead to inability to treat pain with opioid agonists and discontinuation can lead to withdrawal, however, they do not include recommendation for adjusting buprenorphine to an analgesic dose to facilitate opioid based analgesia, while preventing withdrawal.

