### ***Randomization Plan***

Enrolled participants will be randomized 1:1 into one of two groups (defined below). The randomization scheme will be developed using NQuery Software (Statistical Solutions, Boston, MA).and will use permuted blocks of 4 and 6 patients to ensure balance between study arms. The analyst will provide the research coordinator with randomization assignments in sequentially-numbered opaque envelopes (one series of envelopes for each stratum of anticipated post-surgical pain) . The study coordinator will pass the next envelope in sequence to another member of the study team when it is time to assign a subject to a group. Gerbershagen et. al. documented the distribution of pain scores for 179 different surgical procedures and we will use these data to establish randomization strata. For true practice generalizability on the association between buprenorphine management and postsurgical pain control, we will include surgical procedures based on average pain intensity on postoperative day (POD) 1, as opposed to limiting our criteria to a particular surgical type (see Appendix 1).

Patients will be stratified according to their anticipated pain score on POD 1 (4-6/10 range vs >6/10 range) and those within each stratum will be randomized to one of two groups as follows:

- FULL-BUP group: buprenorphine formulation continued throughout the perioperative period
- STD-BUP group: buprenorphine formulation reduced to 16mg the day prior to surgery and then 8mg on the day of surgery onwards. Participants in this group taking 12-16mg buprenorphine at baseline will have no change to their buprenorphine dose on the day prior to surgery.

All participants will be transitioned back to their regular dose of buprenorphine when postoperative surgical pain has subsided as determined by their

buprenorphine provider following hospital discharge. This transition will be coordinated with their buprenorphine provider, which is our current standard practice when buprenorphine is reduced perioperatively.

As the study is unblinded, both patients and providers will be aware of the randomization assignment. To help mitigate bias, the team members collecting and entering data will be masked regarding the patient's assignment. The REDCap database has the randomization assignments in an instrument separate from the study data collection instruments, allowing for data entry without seeing which group the subject is in.

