### ***Biostatistical Analysis***

#### **Sample Size:**

We estimated study size based on postoperative pain scores in a recent study of surgical patients at our institution (manuscript submitted); mean NRS was  $50 \pm 28$ . Our estimate for effect size is based on published data showing that a difference in NRS of 20/100 points is clinically significant. A sample size of 32 per group will have 80% power to detect a difference in means of 20 (the difference between a Group 1 mean,  $m_1$ , of 50 and a Group 2 mean,  $m_2$ , of 30) assuming the common standard deviation is 28 using a two group t-test with a 0.05 significance level. To account for dropout, we will enroll an additional 8 patients for each group for a total sample size of 80 patients.

Statistical Analysis:

Data will be summarized using descriptive statistics and will be presented as means (SD), medians [IQR] or frequency counts (%), as appropriate. Data will be analyzed on an intention to treat basis. We will first examine the success of randomization by comparing covariates demographic and clinical covariate measurements between the FULL-BUP and STD-BUP groups; to conserve study power, no formal statistical comparison will be performed and the data will be reviewed visually. Next we will perform univariate analyses to compare outcome measures between the FULL-BUP and STD-BUP groups, using a two-sided t-test or Mann Whitney U test for continuous variables and chi square or Fisher exact tests for categorical data, as appropriate. For paired analysis of pre/post surgery instruments, we will use McNemar's test or the Wilcoxon test, as appropriate. We will then explore the relationships between demographic and clinical variables and outcome measures in bivariate analyses, using the above methods or Pearson's and/or Spearman's correlation, ANOVA or Kruskal-Wallis test, as appropriate. Finally, we will explore further any observed differences in outcome measures between study arms by adjusting for covariates using analysis of covariance or (in the event of missing data), mixed models regression. Covariates will be entered into the model if they demonstrate a significant ( $p \leq 0.1$ ) association with outcome measures in bivariate analyses.

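### The planned dose difference between arms depends on each patient's baseline buprenorphine dose, but the analysis does not name that dose and a null would be read as applying to every dose

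*Combined protocol and SAP*

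**What the plan says.** Subject Selection admits adults "currently taking buprenorphine formulations equivalent to 12mg or greater for at least the prior 30 days for treatment of OUD". No maximum is given.

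Under Randomization Plan, FULL-BUP has its "buprenorphine formulation continued throughout the perioperative period", and STD-BUP has its "buprenorphine formulation reduced to 16mg the day prior to surgery and then 8mg on the day of surgery onwards". A further rule covers the lower baseline doses: "Participants in this group taking 12-16mg buprenorphine at baseline will have no change to their buprenorphine dose on the day prior to surgery". On stratification the same section says: "Patients will be stratified according to their anticipated pain score on POD 1". Baseline dose is not a stratification factor.

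The Background gives the mechanism at two dose levels. At the upper level: "Therapeutic doses of buprenorphine for OUD treatment (16-32mg) are thought to saturate opioid receptors, rendering further opioid use for analgesia ineffective". At the lower level, imaging is said to suggest that "8mg of buprenorphine is the ideal dose where receptors are available for additional opioid agonists to bind and facilitate analgesia".

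Under Biostatistical Analysis, the arms are first compared without adjustment. Unnamed demographic and clinical variables are then related to the outcomes. Last, observed arm differences are explored further with analysis of covariance or mixed models. On what enters those models: "Covariates will be entered into the model if they demonstrate a significant" association with the outcome, at p ≤ 0.1. The sample size rests on a single difference of 20 points with SD 28.

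The last paragraph of the Background states the intended use. If dose reduction proves no different from full-dose continuation, the institution's guideline can move to continuation without adjustment. No dose limit is attached.

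**The concern.** The two strategies are well defined, but how far apart they are is fixed for each patient before randomisation. One patient is randomised between 12 and 8 mg, another possibly between 32 and 8 mg. The trial estimates the average over whatever mix of doses enrols.

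That average is hard to interpret if it is close to zero. A null could mean that full-dose continuation does not worsen pain. It could also mean that many patients had only a small difference between arms. The guideline statement would apply the result equally to patients on the highest doses, where the Background's worry about blocked analgesia is strongest.

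The analysis as written cannot help separate these readings. Baseline dose may enter as one of the unnamed clinical variables, but only if it happens to correlate with the outcome in these data, and only as a main effect. A main effect adjusts for prognosis. It does not show whether the arm difference changes with the size of the reduction. In addition, the adjusted stage is worded as a follow-up of differences already seen, so it may not be run at all after a null.

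**Working it through.** **Inputs.** Eligibility floor 12 mg (Subject Selection). STD-BUP dose 8 mg from the day of surgery and FULL-BUP dose unchanged (Randomization Plan). Difference 20, SD 28, 32 per arm, significance level 0.05 (Sample Size), with a two-sided t-test (Statistical Analysis). The documents give neither a distribution of baseline doses nor a relation between dose and pain.

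**1. The plan's own figure.** Standardised difference = 20/28 = 0.714. The two-sample t-test needs 31.76, so 32 per arm, and has 80.3% power at 32 per arm. The stated figure reproduces for an average difference of 20.

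**2. Planned difference between arms from the day of surgery** = baseline dose − 8 mg:

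- 12 mg: 12 − 8 = 4 mg
- 16 mg: 16 − 8 = 8 mg
- 24 mg: 24 − 8 = 16 mg
- 32 mg: 32 − 8 = 24 mg

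From 12 to 32 mg this is a six-fold range (24/4). On the day before surgery the arms do not differ for patients on 12 to 16 mg.

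**3. What dilution could do (assumptions, not findings).** Let a share f of patients have a fraction k of a 20-point effect and the rest have all of it. Average difference = 20 × [(1 − f) + k × f]. SD is held at 28, with 32 per arm and two-sided 0.05.

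| f | k = 0: difference, power | k = 0.5: difference, power |
|---|---|---|
| 20% | 16, 61% | 18, 72% |
| 25% | 15, 56% | 17.5, 69% |
| 50% | 10, 29% | 15, 56% |

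The results depend heavily on f and k, and the documents fix neither.

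**4. What a dose-specific analysis could deliver.** Assume that each arm of 32 has 11 patients at 12 mg, 11 at 16 mg and 10 at 24 mg, and that the arm effect is linear in dose. Mean dose is 17.125 and variance 24.23. The standard error of the arm difference at dose d is 28 × √(2/32) × √[1 + (d − 17.125)²/24.23] = 7 × √[1 + (d − 17.125)²/24.23]. With 60 residual degrees of freedom the multiplier is 2.00.

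- 12 mg: SE 10.1, 95% half-width about 20 points
- 16 mg: SE 7.2, about 14 points
- 24 mg: SE 12.0, about 24 points
- Overall comparison: SE 7.0, about 14 points

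For a two-group interaction (20 points against none), SE = 28 × √[2/(32f) + 2/(32(1 − f))]. This is 17.5 at f = 20% and 14.0 at f = 50%, giving about 21% and 30% power by the normal approximation. Dose-specific results would be imprecise at this sample size.

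**The case against.** The strongest reply is that this is a comparison of two strategies in everyone on 12 mg or more. Randomisation balances baseline dose in expectation, so the average effect is an unbiased answer to whether the guideline needs a dose adjustment at all. The 20 points can be read as the difference of interest for the whole enrolled sample, in which case there is nothing to dilute. The Significance section also presents the trial as preliminary to larger studies. All of this stands, and it is why neither the eligibility rule nor the primary comparison needs to change.

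Two stronger readings are tempting. A reader might infer that the protocol contradicts itself, because a patient on 12 mg lies below the saturating range. The documents do not support this. The Background gives 16 to 32 mg as the therapeutic range and says such doses are thought to saturate receptors; it sets no lower threshold. It describes receptors as available at 8 mg and says nothing about 12 mg. The hypotheses do not cite the range either. The day-before rule does not mark such a threshold: it treats 16 mg and 12 mg alike.

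A reader might also infer that the trial is underpowered by a known amount. That would need a dose distribution and a dose-effect relation, and neither is given.

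Two further points count against overreach. Baseline dose could qualify as a clinical variable under the plan, though only as a screened main effect. And part of the document after the statistical section was not available for this review, so the statement that no analysis uses dose is limited to the text available.

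**Conclusion.** The point holds as one of analysis and interpretation. The planned difference between arms runs from 4 mg at a baseline of 12 mg to 24 mg at 32 mg, if patients on that dose enrol. The available analysis text does not name baseline dose, leaves its use to an outcome-driven screen, and states no arm-by-dose term. The intended guideline conclusion carries no dose limit.

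The overall comparison is not biased and the sample size arithmetic is correct. The power figures of 61% and 72% illustrate two assumptions about 20% of patients and do not estimate a shortfall. Dose-specific estimates would be too wide to carry conclusions of their own. Their use is to show how much, or how little, a null says about the higher doses.

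**What to change.** 1. In the adjusted model for the primary outcome, enter baseline buprenorphine dose and the randomisation stratum as pre-specified covariates, exempt from the p ≤ 0.1 screen. Run this model whatever the unadjusted comparison shows.
2. Pre-specify one arm-by-baseline-dose analysis, labelled exploratory. Report the arm difference with a confidence interval at a few stated doses, and tabulate baseline dose by arm.
3. State that the primary result is an average over the doses enrolled, and that a null does not by itself show no difference at the higher doses. Bring the guideline sentence in the Background into line with this.

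The cost is mainly wording, since baseline dose must already be known for eligibility and for the STD-BUP rule. Dose and its interaction use two degrees of freedom, and the stratum one more. The dose-specific intervals will be wide (half-widths of roughly 14 to 24 points under the assumed spread over 12, 16 and 24 mg), so they inform interpretation and are not confirmatory. A linear dose term is also a simplification if the true relation levels off. Eligibility, dosing and sample size are unchanged.

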***Source of subjects, recruitment and retention methods:***

Participants will be recruited when they attend their pre-surgery appointment at the MMC Pre-Operative Readiness Education Program (PREP) clinic. Currently, the majority of patients scheduled for surgery receive consultation from the PREP Clinic, within two months prior to their procedure. Patients who are potentially eligible for the study will be identified by the PREP nurse practitioner or the physician provider who conducts the preoperative evaluation. As part of an IRB reviewed quality improvement project (IRBNet #15892224-1) there is a dashboard in Epic that identifies patients scheduled for surgery who are on buprenorphine. Study staff will review this dashboard to identify potential candidates for this study. The standard practice at MMC is when a patient is identified taking buprenorphine/naloxone through the preoperative chart review, the patient is referred to an anesthesiologist for instructions on the management of buprenorphine/naloxone prior to surgery. Our recruitment method for study participants, therefore, does not differ from this current established practice. A member of study staff will then contact patients by calling the number obtained from the Epic Dashboard. We will introduce the study, and any patient who is interested in learning more about the study and potentially participating will have a consent form sent to them. The informed consent form will be provided electronically, or by mail, for the patient to review. If patient requests the consent be mailed, a follow up phone call will be scheduled. During this phone call, further questions will be answered. Because consent needs to be given prior to day of surgery in order to randomize patients for this trial, we will use DocuSign to obtain consent electronically for patients who would like to participate in the trial.

Patients who choose to participate in the study will receive a phone call within one week prior to their surgery to confirm the buprenorphine management plan that they were assigned (see randomization plan, above). Participant confidentiality will be maintained throughout the consent process.

Participants will be reminded that their involvement in the study is completely voluntary and that they can choose to withdraw from the study at any point. They will also be advised that withdrawing from the study would not affect the care they

receive at MMC. All conversations about their history of OUD and the medications they are taking for treatment will be kept confidential and participating in this study would not cause any additional exposure to their health history outside of standard of care.

To retain participants in this study, they will be reimbursed \$10 for each combined postoperative pain and opioid consumption assessment at POD 0, 1, and 2, and \$60 for completion of the one-month follow-up virtual session. The maximum compensation for participating in this study is \$90 in the form of a reloadable reimbursement card. The appropriate amounts will be loaded at each milestone encounter.

